3.2 PHASE 1 – WEEKS 1-10

3.2.1 Drug Administration {all doses are given orally}

- Week 1
 - (Days 1-3): Valproic acid - 500 mg every evening
 - (Day 4-7): Valproic acid - 500 mg twice daily (morning and evening)
- Weeks 2 through 10
 - Valproic acid – 500 mg every morning and 1000 mg every evening

Drug will be dispensed at each clinic visit and include the number of capsules necessary to be administered through the next scheduled clinic visit plus 4 days. Patients will be instructed to take the medications at the same time each day, with or without food. Prior to discharge from the clinic, the research nurse will review the following information with the patient:

- The toxicities of the agent and how to treat/prevent them
- The signs and symptoms to report to the study team
- How to complete the patient diary

3.2.2 Valproic acid levels

Blood samples will be collected prior to dosing (trough levels) weekly from weeks 2 to 10 and week 12 for patients on Schedule 2. The patient will be asked to refrain from taking the morning dose of valproic acid and will be instructed to bring in the morning dose along with the rest of valproic acid pills for a pill count.

3.2.3 Dose Modification

Based on the serum valproic acid trough level, the dose of valproic acid will be titrated as noted below to maintain serum trough levels between 50 and 100 $\mu\text{g}/\text{ml}$. Any change of the dose of valproic acid will require repeat serum trough levels within 3 days as described above.

- If the serum trough level is $> 100 \mu\text{g}/\text{ml}$, the dose will be reduced by 125 to 500 mg depending on the serum level
- If the serum trough level is $< 50 \mu\text{g}/\text{ml}$, the dose will be increased by 125 to 500 mg depending on the serum level
- For persistent grade 2 toxicities, the dose will be adjusted at the discretion of the PI
- For grade 3 or greater toxicities, the dose will be held until the toxicity has resolved to grade 1 or baseline. Following resolution, the dose will be reduced

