3.3 EVALUATIONS WEEKS 1-10 {ALL EVALUATIONS ARE +/- 3 DAYS}

- Week 2-10:
 - Serum valproic acid levels may be performed weekly on all patients for at least the first 4 weeks of treatment.
 - Reports from all evaluations performed at outside institutions will be faxed to:

[name] or [name]
[contact]

This includes lab values, physical exams, patient diaries, etc.

- Week 2 (Day 10):
 - Physical exam including ECOG status
 - CBC with differential, platelets, BUN, creatinine, total protein, total bilirubin, ALT, AST, ALKP, amylase, ammonia, albumin and b-HCG (if applicable).
 - Toxicity assessment, pill count, and review of diary
- Week 4 – may be performed by their primary physicians
 - Physical exam including ECOG status
 - CBC with differential, platelets, BUN, creatinine, total protein, total bilirubin, ALT, AST, ALKP, amylase, ammonia, albumin and b-HCG (if applicable).
 - Toxicity assessment, pill count, and review of diary

- Week 6:
 - Physical exam including ECOG status
 - CBC with differential, platelets, BUN, creatinine, total protein, total bilirubin, ALT, AST, ALKP, amylase, ammonia, albumin and b-HCG (if applicable).
 - Toxicity assessment, pill count, and review of diary
- Week 8 - may be performed by their primary physicians
 - Physical exam including ECOG status
 - CBC with differential, platelets, BUN, creatinine, total protein, total bilirubin, ALT, AST, ALKP, amylase, ammonia, albumin and b-HCG (if applicable).
 - Toxicity assessment, pill count, and review of diary
- Week 10:
 - Physical exam including ECOG status
 - CBC with differential, platelets, BUN, creatinine, total protein, total bilirubin, ALT, AST, ALKP, amylase, ammonia, albumin and b-HCG (if applicable).
 - Serum valproic acid levels.
 - Toxicity assessment, pill count, and review of diary
 - Tg, TSH
 - Thyrogen Scan
 - Health Related Quality of Life HRQOL) form completion
 - Tumor tissue biopsy of any accessible lesions (Section 3.7)
 - 24 hour urinary iodine level

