3.9 CRITERIA FOR REMOVAL FROM PROTOCOL THERAPY AND OFF STUDY CRITERIA

3.9.1 Criteria for removal from protocol therapy

- Patient request
- PI discretion, if the PI feels it is not in the best interest of the patient to remain on treatment
- Liver Dysfunction (enzyme levels above 1.5 times ULN)
- Platelet < 50,000
- Ammonia levels > 65 mol/l
- Progressive disease
- Pregnancy
- Pancreatitis (amylase level above 1.5 ULN)
- Alcohol consumption
- Other unacceptable toxicities as determined by the PI

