8.3 DATA AND SAFETY MONITORING PLAN

Clinical Trial Monitoring Plan

Data will be entered in C3D by the data manager assigned to the protocol. The research nurse will verify 100% of the e-CRFs for one of the first 3 patients enrolled. Subsequent monitoring will be conducted by the Research Nurse as described in the table below. Any significant discrepancies will be discussed with the PI and the study team and a corrective action plan will be drafted and shared with the team. AEs on all patients are discussed at the weekly team meeting to assess over all safety and to ensure that all reporting requirements are met.

*Based on expected accrual, 25% of enrolled patients will be monitored.

Time of year	Evaluation	# of records monitored
Quarterly	Compare all fields of the following e-CRFs to the source documentation: Eligibility, Surgical Procedure, Course Assessment, Adverse Events, Off Treatment	3-5 study patients

Careful evaluation to ascertain the toxicity and clinical response will be performed. The principal investigator will monitor the data and toxicities to identify trends quarterly. The principal investigator will be responsible for revising the protocol as needed to maintain safety.

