9.1.6 Toxicity

- Hepatotoxicity
- Teratogenicity in the fetus of pregnant women. At high doses (>90mg/kg/day), valproic acid has been shown to reduce spermatogenesis and induce testicular atrophy in dogs.
- Hyperammonemia has been reported independent of abnormal liver function tests.
- CNS depression and somnolence. Because of the potential interactions of valproic acid with other CNS depressants, alcohol will be prohibited while patients are on the study. If a patient does drink alcohol, he or she will be removed from the study.
- Nausea, vomiting, anorexia, increases appetite and indigestion
- Thrombocytopenia
- Pancreatitis

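### Section 3.2.3 does not rank the grade 3 toxicity reduction against the below-50 µg/ml increase, so in a low-trough subgroup it can order re-escalation and does not bar a return to the toxic dose

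*Protocol*

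**What the plan says.** Protocol section 3.2.3 lists four dose rules side by side, with the stated aim of keeping the trough between 50 and 100 µg/ml. Two of them matter here.

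- Trough below 50 µg/ml: "the dose will be increased by 125 to 500 mg depending on the serum level".
- Grade 3 or greater toxicity: dosing stops until the event settles to grade 1 or baseline, and then "Following resolution, the dose will be reduced". The size of that reduction, how long it lasts and any later maximum are not given.

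The same section adds: "Any change of the dose of valproic acid will require repeat serum trough levels within 3 days as described above". Further troughs may follow on the weekly schedule, but the protocol is not uniform about it. Section 3.2.2 says "Blood samples will be collected prior to dosing (trough levels) weekly from weeks 2 to 10", while section 3.3 says "Serum valproic acid levels may be performed weekly on all patients for at least the first 4 weeks of treatment".

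Within section 3.2.3, discretion over the dose is given to the PI only for persistent grade 2 toxicity. Section 3.9.1 lists reasons to remove a patient from therapy: liver enzymes, amylase, platelets, ammonia, PI discretion, and "Other unacceptable toxicities as determined by the PI". Section 8.3 adds that "AEs on all patients are discussed at the weekly team meeting".

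**The concern.** Both rules are mandatory, and no text says which one governs when both apply. A toxicity reduction is itself a dose change, so it always leads to a repeat trough within three days. If that trough is below 50 µg/ml, a clinician who follows the section literally must raise the dose of a patient who has just been reduced for grade 3 toxicity. No ceiling stops the dose at a level under the one that caused the event.

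The patients exposed are those kept on drug after a grade 3 event that section 3.9.1 does not catch. Section 9.1.6 lists "CNS depression and somnolence", and also nausea and vomiting; none of these has its own removal threshold. What is at stake is patient safety in that subgroup. The type I error, power, sample size and response decision are untouched.

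**Working it through.** The plan gives no figure to reproduce here, so the check is dose arithmetic on the rules.

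**Inputs from the protocol.** Standard dose in weeks 2–10: 1500 mg/day (section 3.2.1). Increase step: 125–500 mg when the trough is below 50 µg/ml (3.2.3). Expected plasma concentration: 0.4–0.6 mM at 500 mg twice daily, i.e. 1000 mg/day (1.3).

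**Assumptions.** The toxicity cut *c* is 125–500 mg, borrowed from the level-based steps because the protocol gives no size. Trough is proportional to dose. Molecular weight is 144.21.

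**When is an increase ordered?** With earlier trough T at dose D, the trough after the cut is T × (D − c)/D. It is below 50 if T < 50 × D/(D − c). For D = 1500:

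| Cut (mg) | Dose after cut (mg/day) | Increase ordered if T is below (µg/ml) | Dose after one permitted increase (mg/day) |
|---|---|---|---|
| 125 | 1375 | 50 × 1500/1375 = 54.5 | 1500–1875 |
| 250 | 1250 | 50 × 1500/1250 = 60.0 | 1375–1750 |
| 375 | 1125 | 50 × 1500/1125 = 66.7 | 1250–1625 |
| 500 | 1000 | 50 × 1500/1000 = 75.0 | 1125–1500 |

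In every row the largest permitted step reaches 1500 mg/day or more.

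**When is full return compelled?** With the smallest steps (125 mg), the dose gets back to 1500 only if the trough at 1375 is still below 50, i.e. T < 54.5. Paths after a 500 mg cut (trough in brackets):

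- T = 54: 1000 (36.0), 1125 (40.5), 1250 (45.0), 1375 (49.5), 1500 (54.0). Full return.
- T = 56: 1000 (37.3), 1125 (42.0), 1250 (46.7), 1375 (51.3). Stops.
- T = 60: 1000 (40.0), 1125 (45.0), 1250 (50.0). Stops.
- T = 70: 1000 (46.7), 1125 (52.5). Stops.

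From 54.5 up to the limit in the table, full return needs a larger chosen step.

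**Patient already up-titrated.** Trough 48 at 1500, raised to 1625, gives 48 × 1625/1500 = 52.0. A grade 3 event occurs and the dose goes back to 1500, where the trough is again 48. The smallest ordered increase restores 1625. This holds after a single 125 mg up-step. After a larger up-step cut back in full, an increase is still ordered, but not necessarily the whole way.

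**Patient already reduced for a high level.** If the trough exceeded 100 at 1500 and the dose was cut to 1000, then T at 1000 exceeds 100 × 1000/1500 = 66.7. The limits at D = 1000 are 57.1 (c = 125), 66.7 (250), 80.0 (375) and 100 (500). Cuts of 125 or 250 mg therefore never trigger the rule. A 375 mg cut triggers it for T of 66.7–80, and a 500 mg cut for 66.7–100. Steps of 125 mg then stop at 625–750 mg/day: T = 67 gives 500 (33.5), 625 (41.9), 750 (50.3); T = 80 gives 500 (40.0), 625 (50.0). Compelled return to 1000 would need T < 50 × 1000/875 = 57.1, which cannot occur here.

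**Typical patient.** 0.4–0.6 mM × 144.21 = 57.7–86.5 µg/ml at 1000 mg/day. Multiplied by 1.5, this is 86.5–129.8 at 1500. Even a 500 mg cut from 1500 leaves 57.7–86.5, above 50. The compelled case (below 54.5 at 1500) corresponds to 54.5/1.5 = 36.4 µg/ml at 1000 mg/day, and 36.4/144.21 = 0.25 mM, well under 0.4.

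**The case against.** The strongest reply is that a clinician would let the specific toxicity instruction override routine titration, so this is only drafting. There are also brakes. Many hepatic, pancreatic, platelet and ammonia events end therapy under section 3.9.1, and the PI can remove anyone else. Adverse events are reviewed weekly. Within section 3.2.3, persistent grade 2 toxicity allows an adjustment, a recurrent grade 3 event brings another hold and cut, and a trough above 100 brings a reduction. The increase is sized to the serum level, so a 500 mg step for a trough just under 50 would be an odd choice. The section belongs to weeks 1–10; from week 11 patients on Schedule 2 keep their dose. Section 9.1 also points to the package insert, which is not shown here.

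Most of this stands, and it makes the group small. It does not close the gap. Removal criteria say nothing about dose for patients who stay on drug, and the hold-and-reduce rule presupposes that such patients exist. The other brakes act only once toxicity persists or recurs, or on high levels. PI discretion over dose is written for grade 2, not grade 3.

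A reader might infer that the three-day recheck produces a conflict in every case. It does not: the recheck is always required, but the rules collide only if the result is below 50. A reader might also infer that an ordinary patient is at risk because the limits of 54.5–75 lie inside the 50–100 target. The section 1.3 figures put the typical patient above those limits at 1500 mg/day. That reassurance is approximate, since section 1.3 gives plasma concentrations rather than troughs, and it covers one cut from 1500 only.

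**Conclusion.** The point holds as a minor patient-safety correction. As written, section 3.2.3 can order an increase of 125–500 mg soon after a grade 3 toxicity reduction, and it does not forbid reaching the toxic dose again. This is confined to low-trough patients who remain on drug after a grade 3 event outside the section 3.9.1 removals.

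The limits for some increase (54.5–75 µg/ml at 1500 mg/day) rest on proportionality and on an assumed cut of 125–500 mg. If troughs fall less than proportionally the limits move down towards 50; if more steeply, they move up. The lack of precedence itself depends on neither assumption.

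It would go too far to say that the protocol generally forces patients back to the toxic dose. That is compelled only for earlier troughs below about 54.5 µg/ml at 1500 mg/day, or after a 125 mg up-titration for a low trough is reversed. Elsewhere it is permitted, not required. How many patients would be affected cannot be derived from the protocol.

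**What to change.** Add to section 3.2.3:

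> *After a dose reduction for grade 3 or greater toxicity, the below-50 µg/ml increase rule no longer applies automatically; any later increase is at PI discretion and must stay below the dose at which the toxicity occurred.*

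This settles the precedence, sets a ceiling, and makes clear that partial increases remain possible. The cost is one sentence. The downside is that some patients will stay below the 50–100 µg/ml target, which is a reasonable price after grade 3 toxicity. No endpoint, analysis or sample size changes.

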3.2.4 Protocol stopping rules

If more than 15% of patients withdraw from the study due to grade 3 toxicity, a safety endpoint will be reached and the study will be closed to accrual. The stopping rule applies to all subjects during the entire treatment and follow up period of the study.

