 - CBC with differential, platelets, BUN, creatinine, total protein, total bilirubin, ALT, AST, ALKP, amylase, ammonia, albumin and b-HCG (if applicable).
 - Toxicity assessment and review of diary
- Week 16:
 - Physical exam including ECOG status
 - CBC with differential, platelets, BUN, creatinine, total protein, total bilirubin, ALT, AST, ALKP, amylase, ammonia, albumin and b-HCG (if applicable).
 - Tg, TSH
 - Toxicity assessment and review of diary
 - Ultrasound of the neck and mediastinum
 - MRI or CT of the neck and chest
 - FDG-PET scan
 - Health Related Quality of Life HRQOL) form completion
- Weeks 17-52
 - Patients who show a response by RECIST criteria or have a decreased thyroglobulin level from Day 1 of the treatment (registered as a partial response to the treatment) will continue on valproic acid at their current dose for a total of 52 weeks.

- Stop valproic acid if no response
- Sixteen weeks or 4 months is significant amount of time to measure response to treatment and therefore, if there is a response, a patient's thyroglobulin levels should have decreased by then, as well as, by RECIST criteria.
- Patients who show no response, patients will stop valproic acid treatment and continue with routine follow up.

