3.8 FOLLOW UP FOR ALL PATIENTS {FROM WEEK 17}

- 3 months
 - Physical exam including ECOG status
 - CBC with differential, platelets, BUN, creatinine, total protein, total bilirubin, ALT, AST, ALKP, amylase, ammonia, albumin.
 - CT and/or MRI of the chest
 - Health Related Quality of Life HRQOL) form completion
 - Ultrasound of the neck as indicated
 - Tg, TSH
- 6 months
 - Physical exam including ECOG status
 - CBC with differential, platelets, BUN, creatinine, total protein, total bilirubin, ALT, AST, ALKP, amylase, ammonia, albumin..
 - Tg, TSH
 - Health Related Quality of Life HRQOL) form completion
- 9 months - for patients continuing on valproic acid only-
 - Physical exam including ECOG status
 - CBC with differential, platelets, BUN, creatinine, total protein, total bilirubin, ALT, AST, ALKP, amylase, ammonia, albumin.
 - Tg, TSH
 - Health Related Quality of Life HRQOL) form completion

- 12 months
 - Physical exam including ECOG status
 - CBC with differential, platelets, BUN, creatinine, total protein, total bilirubin, ALT, AST, ALKP, amylase, ammonia, albumin.
 - CT and/or MRI of the chest
 - Ultrasound of the and neck
 - Tg, TSH
 - Health Related Quality of Life HRQOL) form completion

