3.9.2 Off-study Criteria

- Completion of the follow up period
- Patient request
- PI discretion ,if the PI feels it is not in the best interest of the patient to remain on treatment

Note: Patients must remain on study until all study related adverse events have resolved to grade 2 or less or baseline.

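### The 15% safety stop in section 3.2.4 counts withdrawal from the study, so a patient taken off valproic acid for grade 3 or greater toxicity who stays in follow-up is, read literally, not counted

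*Protocol*

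**What the plan says.** Section 3.2.4 of the protocol gives the rule: "If more than 15% of patients withdraw from the study due to grade 3 toxicity, a safety endpoint will be reached", with closure to accrual as the consequence. It adds: "The stopping rule applies to all subjects during the entire treatment and follow up period of the study". Section 6.2 explains the 15% as the acceptable rate of grade 3 toxicity.

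The protocol handles the end of treatment and the end of study participation under separate headings.

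- **3.9.1, removal from protocol therapy.** Toxicity is listed here: limits for liver enzymes, platelets, ammonia and amylase, and "Other unacceptable toxicities as determined by the PI".
- **3.9.2, off study.** The reasons are completion of follow-up, patient request and PI discretion. Toxicity is not named. A note adds: "Patients must remain on study until all study related adverse events have resolved to grade 2 or less or baseline".

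Staying on study after the drug stops is an ordinary path. Section 3.8 sets out follow-up for all patients and reserves only the 9-month visit "for patients continuing on valproic acid only". Section 3.5.2 says of non-responders that "patients will stop valproic acid treatment and continue with routine follow up".

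Section 3.2.3 prescribes hold and dose reduction for toxicity of grade 3 or greater, whereas 3.2.4 names grade 3 only.

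**The concern.** A rule meant to cap toxicity should count toxicity. As worded, it counts an exit that the protocol does not list toxicity as a reason for. A patient with an unresolved related grade 3 event is even told to remain in the group that the wording leaves out.

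This is the only trial-level safety rule in the protocol with a number that closes accrual. Weekly discussion of adverse events, quarterly PI review (8.3) and IRB continuing review (8.2.2) would bring the events to light, but none of them says at what count the trial stops. If two people can apply 3.2.4 to the same patients and reach opposite answers, the rule does not do its job when it is needed.

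**Working it through.** **1. No operating characteristics to reproduce.** The protocol states the 15% threshold without a false-stop probability, a detection probability or a schedule of looks. The response design in 6.2 is separate, and its stated figures reproduce (type I error 0.0736, power 0.903).

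**2. What the threshold means in patients.** The stop needs the smallest k with k/n > 0.15.

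| Patients n | Count needed k |
|---|---|
| 1–6 | 1 |
| 7–13 | 2 |
| 14–19 | 3 |
| 20–25 | 4 |

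Checks: 2/13 = 15.4%; 3/20 = 15.0%, which does not exceed 15%; 4/25 = 16.0%.

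**3. Same data, two readings.** Suppose 4 of 20 patients are permanently taken off drug for grade 3 toxicity and 2 of the 4 stay in follow-up.

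- Counting removal from therapy: 4/20 = 20%, above 15%, close.
- Counting withdrawal from the study: 2/20 = 10%, below 15%, continue.

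This needs no assumption about rates. It shows that the reading decides the outcome.

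**4. Illustration of the probabilities.** The protocol gives neither a toxicity rate nor the share of such patients who would also leave the study. Both are assumed here: a true rate t of treatment-ending grade 3 or greater toxicity of 20% or 30%, and a counted share f of 1 or 0.5. The counted rate is p = t × f, so half counting turns 20% into 10% and 30% into 15%.

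- Single look at 25: P(X ≥ 4), X ~ Binomial(25, p).
- Check after each patient from patient 7: binomial recursion over n up to 25, stopping at the first n ≥ 7 with count at or above k in the table. Each outcome is taken as known before the next patient is counted.

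| Counted rate p | Single look at 25 | After each patient from the 7th |
|---|---|---|
| 0.10 | 0.236 | 0.447 |
| 0.15 | 0.529 | 0.707 |
| 0.20 | 0.766 | 0.869 |
| 0.30 | 0.967 | 0.984 |

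With half counted rather than all, the chance of stopping at a true 20% falls from 0.766 to 0.236 (single look) or from 0.869 to 0.447 (from patient 7). At a true 30% it falls from 0.967 to 0.529 or from 0.984 to 0.707. With f = 1 there is no loss; with f = 0 the rule never triggers. The loss therefore runs from nothing to everything, depending on a share that the documents do not give.

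**5. Why a first look is needed.** By the table in step 2, one event among the first six patients exceeds 15%. Checked from patient 1, the recursion gives a chance of closing of 0.31 at a true rate of 5%, 0.589 at 10% and 0.792 at 15%.

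**The case against.** The best defence is that the authors use study and treatment loosely and meant withdrawal from treatment. There is real support for this. PI discretion appears in 3.9.2 as an off-study reason, yet it is worded "if the PI feels it is not in the best interest of the patient to remain on treatment". Section 9.1.6 has a patient who drinks alcohol removed from the study, although 3.9.1 lists alcohol as a reason to end therapy. Section 3.2.4 follows directly after dose modification, and its second sentence brings the follow-up period within the rule. On this reading nobody is missed. What stands is that the intent may well be broader than the words. But loose use elsewhere shows that the term is ambiguous, not which reading governs a rule that closes accrual. The follow-up sentence fixes the period and the population, not the event to be counted.

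Second, the laboratory limits in 3.9.1 carry no grade. A removal for liver enzymes above 1.5 times the upper limit of normal need not be a grade 3 event, so it need not count under either reading. This stands: the 3.9.1 list is no measure of how many patients the wording would miss.

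Third, closing accrual does not change the care of enrolled patients, who are covered by dose holds, reductions and the removal criteria. That limits the harm but does not settle when enrolment should end.

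A reader might go further and infer that the safety stop is inert, or that a particular number of extra patients would be exposed. The documents do not support that. A patient who leaves by request or at PI discretion because of toxicity is counted even literally, and any count of extra patients would need an assumed toxicity rate, an assumed share and an assumed checking schedule.

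**Conclusion.** The point holds as a defect of wording. Section 3.2.4 counts leaving the study, while the protocol's own structure places treatment-ending toxicity under removal from therapy and normally keeps such patients on study. The literal rule can therefore give the wrong accrual decision against the purpose stated in 6.2, as the 20% versus 10% example shows.

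Its size in practice is unknown and may be zero. The probabilities in the working are illustrative: they rest on assumed rates of 20% to 30%, an assumed half counted and, for the repeated check, immediate outcomes. Section 3.2.4 sets no schedule of looks, and its rule extends through follow-up, so outcomes would often arrive later than the calculation supposes.

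The difference between grade 3 in 3.2.4 and grade 3 or greater in 3.2.3 is editorial. A rule that stops for grade 3 and ignores grade 4 is not a plausible intention, but the same rewording can settle it.

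**What to change.** Replace the trigger sentence in 3.2.4 with:

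> *If, once at least 7 patients have been treated, more than 15% of treated patients have been permanently removed from protocol therapy, or have withdrawn from the study, because of grade 3 or greater toxicity, accrual will close.*

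This names the event, the denominator, the grades and the first look. Section 3.2.3 needs no change, and neither do the sample size and response analysis.

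The cost is that the stop is reached more often than under the literal wording. With all such patients counted and a check after each patient from the seventh, accrual closes with probability about 45% at a true 10% rate and 71% at 15%. At a single look at 25 the figures are 24% and 53%. Starting at patient 7 prevents one early event from closing the trial, but the chance of stopping at rates at or below 15% remains substantial. The sponsor should accept that knowingly when confirming the threshold and how often it is checked.

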6.2 SAMPLE SIZE AND POWER ANALYSIS

This is a phase II study aimed at measuring the impact of valproic acid on iodine uptake and on tumor response. Response will be defined as complete or partial response as outlined in section 5.2. The study uses a two-stage Simon optimal design with an interim analysis planned when 13 patients are evaluable for response. If no complete/partial responses are seen at that time the study will close to accrual. The study will proceed to stage II if at least one response is seen among the first 13 patients. At the end of study, if the cumulative number of responses among the 20 evaluable patients is 3 or more, valproic acid will be considered efficacious, while this will not be the case if 1-2 responses are noted. Under the null hypothesis of a true response rate that does not exceed 5% ($p_0=0.05$), the two-stage design will control type I error (α) to be no more than 7.4%, and when the true response rate is at least 25% ($p_1=0.25$), the study has at least 90% power ($\beta=0.10$). The probability of triggering early stopping is at least 51% if the true response rate is 5% or less, and less than 2.5% if the true response rate is 25% or more. If the accrual is stopped at the first stage due to futility, the upper bound of a 95% confidence interval for the response rate will be less than 25%. We will plan to enroll up to 25 patients with the expectation that 20 patients (80%) will be evaluable for response.

The stopping rule for Grade 3 toxicity is set at 15% as the acceptable toxicity rate because the study is designed to detect a treatment efficacy rate of 15% or higher. Therefore, if the acceptable toxicity rate is higher than the expected efficacy rate the study will be stopped.

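### The toxicity stopping rule (3.2.4) counts withdrawals from the study, so as written it can miss, or count late, patients who stop valproic acid for toxicity and stay in follow-up

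*Protocol*

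**What the plan says.** Section 3.2.4 sets the trigger: "If more than 15% of patients withdraw from the study due to grade 3 toxicity, a safety endpoint will be reached", after which accrual closes. A second sentence extends the rule to all subjects through treatment and follow-up. Section 6.2 refers to the same limit in other terms: "The stopping rule for Grade 3 toxicity is set at 15% as the acceptable toxicity rate".

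The handling of individual patients is set out elsewhere:

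- **3.2.3:** "For grade 3 or greater toxicities, the dose will be held until the toxicity has resolved to grade 1 or baseline", followed by a reduced dose.
- **3.9.1** (removal from protocol therapy): limits for liver enzymes, platelets, ammonia and amylase, none tied to a toxicity grade, and "Other unacceptable toxicities as determined by the PI".
- **3.9.2** (off study): a separate list of completed follow-up, patient request and PI discretion. A note adds: "Patients must remain on study until all study related adverse events have resolved to grade 2 or less or baseline".
- **3.8:** follow-up is headed as being for all patients. Only the 9-month visit is "for patients continuing on valproic acid only".
- **3.5.2:** for non-responders, "patients will stop valproic acid treatment and continue with routine follow up".

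**The concern.** The protocol separates leaving therapy (3.9.1) from leaving the study (3.9.2). Toxicity is named only in the first list, yet the stopping rule is worded in terms of the second. A patient taken off valproic acid for a grade 3 event who then attends follow-up has not withdrawn from the study. Read literally, that patient does not count towards the 15%.

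What is at stake is when accrual closes. The limits in 3.9.1 protect individuals. Weekly adverse event discussion and quarterly PI review (8.3) and IRB reporting (8.2) continue, but none of these carries a trial-level threshold. If the one rule that does can be counted in more than one way, the same patients may or may not close the trial.

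**Working it through.** **No stated figure to reproduce.** The protocol gives no operating characteristics for the toxicity rule. The efficacy figures in 6.2 do reproduce (type I error 0.0736, power 0.903) and are not at issue.

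**Which event is counted.** Take a patient with a related grade 3 event under each reading.

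| Course of the patient | 3.2.4, literal (off study) | Off therapy | 6.2, toxicity rate |
|---|---|---|---|
| Dose held, resumed lower (3.2.3) | not counted | not counted | counted |
| Drug stopped, stays in follow-up (3.9.1, 3.8) | not counted | counted | counted |
| Drug stopped, later goes off study because of the toxicity | counted, usually only once the event is grade 2 or less or baseline (3.9.2 note) | counted at the stop | counted at onset |

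The three readings agree only eventually, and only for the third patient. The denominator of the 15% (enrolled, treated or evaluable) is not stated either.

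**Thresholds.** The smallest count above 15% of n patients is 1 for n = 1–6, 2 for n = 7–13, 3 for n = 14–19 and 4 for n = 20–25. For example, 1/6 = 16.7% exceeds 15%, 1/7 = 14.3% does not, and 3/20 is exactly 15%.

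**Illustration of direction only.** Let p be the true rate of removal for grade 3 or greater toxicity and s the share of those patients whom the rule counts. Both are assumptions, because the protocol gives neither. The counted-event probability is q = p × s. Among trials not yet stopped, the recursion is P_n(k) = P_{n−1}(k)(1 − q) + P_{n−1}(k − 1)q. The trial stops at the first n ≥ 7 with k/n > 0.15, and unstopped trials run to 25 patients (maximum enrolment, 6.2). Each outcome is taken as known before the next patient enters.

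| Assumed p | s = 1 | s = 0.75 | s = 0.5 | s = 0.25 |
|---|---|---|---|---|
| 0.30: stopping probability (mean enrolled) | 0.98 (8.6) | 0.92 (10.6) | 0.71 (14.7) | 0.30 (20.8) |
| 0.20: stopping probability (mean enrolled) | 0.87 (11.7) | 0.71 (14.7) | 0.45 (18.6) | 0.15 (22.8) |

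A single look at 25 patients (at least 4 counted) gives the same direction with different values: at p = 0.30, 0.97 for s = 1, 0.53 for s = 0.5 and 0.11 for s = 0.25. The delay from the 3.9.2 note cannot be put into numbers, because no resolution times are given.

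**How the repaired rule would behave.** The same recursion with every event counted (s = 1):

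| True rate | Checked from patient 7 | Checked from patient 1 |
|---|---|---|
| 5% | 0.15 | 0.31 |
| 10% | 0.45 | 0.59 |
| 15% | 0.71 | 0.79 |

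Without a minimum number, one event among the first six patients closes accrual. At a true 5% that alone has probability 1 − 0.95^6 = 0.26.

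**The case against.** The strongest reply is that this is loose terminology and that everyone would read 3.2.4 as leaving treatment. The text gives that real support. The PI-discretion criterion for going off study asks "if the PI feels it is not in the best interest of the patient to remain on treatment", so a PI who stops the drug for toxicity arguably meets an off-study criterion too. Section 9.1.6 removes a patient who drinks alcohol from the study, while 3.9.1 lists alcohol under removal from therapy. This stands: removal from treatment was probably intended. It does not settle the matter, because 6.2 points to a third event and nothing tells the PI which to count.

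A second reply is that 3.2.4 covers all subjects through follow-up. That fixes who is in scope, but it leaves the counted event unchanged.

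Three stronger readings are tempting and are not supported:

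- **The rule can never trigger.** Patients can leave the study by request or at PI discretion, and the 3.9.2 note delays an exit without forbidding it.
- **Grade 4 and 5 events are exempt.** The rule names only grade 3, but 3.2.3 speaks of grade 3 or greater, and exempting worse events is not a plausible intention. The wording should simply say so.
- **A definite number of extra patients would be exposed.** Every figure in the illustration depends on assumed rates, counted shares and a first look that the protocol does not give.

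**Conclusion.** The point holds as a defect of definition. Sections 3.2.4, 3.9 and 6.2 do not name the same event. Followed literally, 3.2.4 can omit or delay patients who stop valproic acid for toxicity and remain in follow-up. This conclusion rests on the text alone. The calculations show that the choice of event can matter a great deal in a trial of 25, but they do not estimate the undercount.

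The efficacy analysis is unaffected, and the individual safeguards and regular safety reviews limit the consequence. It should still be corrected, because this is the protocol's only numerical limit for closing accrual on toxicity and the repair is cheap. Confidence is moderate, given the probable intention.

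**What to change.** Reword 3.2.4 along these lines:

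> Once at least 7 patients have been treated, accrual closes if more than 15% of all patients treated to date have been removed from protocol therapy, have gone off study or have died because of a grade 3 or greater toxicity at least possibly related to valproic acid. Each patient counts from the date of the decision to stop the drug, or of death if earlier.

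Refer to this same event in 6.2. Seven is an example: it is the first point at which two events are needed. The sponsor should choose the minimum knowing the stopping probabilities above, including about 0.71 at a true 15%, the rate that 6.2 calls acceptable.

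The cost is wording in two sections. Events are already graded (5.3), related grade 3 and 4 events are already tabulated for the IRB (8.2.2), and an Off Treatment form is already in use (8.3). The downside is a rule that triggers more readily than its literal wording. Two groups would still not count: patients removed under a 3.9.1 laboratory limit for an event below grade 3, and patients who resume at a reduced dose. The second group would count if the sponsor adopts the broader toxicity-rate reading of 6.2, in which case 3.2.4 should say so.
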